1.2. Information on the study drug

HEDUSSIN® (active substance: dry ivy leave extract).

HEDUSSIN[®] is recommended for use in treatment of wet cough of various aetiology as an agent facilitating expectoration – expectorant – in both adults and children. The medicine is administered orally and should be shaken before use.

In children aged 2-5, it is recommended to administer 2 ml of the syrup twice daily (which corresponds to 33 mg of dry ivy leave extract daily).

In children aged 6-12, it is recommended to administer 4 ml of the syrup twice daily (which corresponds to 66 mg of dry ivy leave extract daily).

In adults and children above the age of 12, it is recommended to administer 6 ml of the syrup twice daily (which corresponds to 99 mg of dry ivy leave extract daily).

Contraindications for the use of the dry extract of ivy leaves include:

- Hypersensitivity to the active substance, other plants from the Araliaceae family or any of the
 excipients (non-crystallizing liquid sorbitol, potassium sorbate, xanthan gum, anhydrous citric
 acid)
- Age below 2 years.

Persistent or recurring cough in children aged 2 to 4 requires a thorough diagnostic before the commencement of the treatment.

In case of the occurrence of dyspnoea, fever or purulent sputum, one should seek advice from a doctor or pharmacist.

It is not recommended to administer the **HEDUSSIN**^R syrup concomitantly with antitussive medicine such as codeine or dextromethorphan. Caution is recommended when administering the syrup in Patients suffering from gastritis or the peptic ulcer disease.

The HEDUSSIN® syrup contains sorbitol, therefore it should not be used by Patients with rare inherited fructose intolerance disorders.

There is no data on the influence of the medicinal product on fertility. The usage safety during pregnancy and breastfeeding has not been established. Therefore, it is not recommended to use the product during that time.

The research on the influence of the preparation on the ability to operate machines has not been conducted.

Interactions with other medicinal products and other forms of interactions

No research conducted.

Study number: EUP/HED/008/2016

VERSION DATE: 21.11.2016

Adverse effects resulting from the use of the HEDUSSIN® medicinal product include:

- Very common (≥ 1/10): none
- Common (≥1/100 to <1/10): nausea, vomiting, diarrhoea
- Uncommon (≥1/1000 to <1/100): allergic reactions (hives, skin rash, angioedema, dyspnoea)

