2. THE AIM OF THE STUDY

2.1. The main aim of the Study

The assessment of the efficacy of the **HEDUSSIN**® medicinal product use in the treatment of productive (wet) cough evaluated on the basis of the severity and the treatment time of the infection occurring with a productive (wet) cough of various aetiologies in children aged 2-12.

The assessment of the efficacy of the **HEDUSSIN®** medicinal product will be based on:

- 1. Observation of the below symptoms and changes in their intensity during the treatment*:
 - The severity of the cough (from 0 to 4)
 - Dyspnoea (from 0 to 4)
 - Auscultatory changes (wheezing, dry rale, crackles) (from 0 to 4)
 - Chest pain during cough (from 0 to 4)
 - Hoarse breathing (from 0 to 4)

0- absent; 1- mild; 2- moderate; 3- severe; 4- very severe

- 2. Determination of the infection duration (measured in days)
- 3. Evaluation of the body temperature
- 4. The use of concomitant treatment:
 - The inclusion of an antibiotic
 - The inclusion of other medications and dietary supplements

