8.4. Concomitant medication

Data on other drugs used concomitantly with the HEDUSSIN® medicinal product will be recorded in the Study Questionnaire (SQ) during each control assessment.

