10.4.3. Adverse effects analysis

This Study is an efficacy assessment study (PAES) and its main aim is not focused on the research of the medicinal product safety – especially, the analysis of the reported adverse events will be conducted in a general manner as an auxiliary analysis in relation to the main aim of the Study, i.a. the efficacy assessment. The details on the safety of the used treatment contained within the Study Questionnaires will be included in the summaries of data on individual patients. Analysis and summary tables will be based on data from the study population taking into account the duration of exposure to the medicinal product under investigation.

All adverse effects will be coded in accordance with Medical Dictionary for Regulatory Activities (**MedDRA**).

The prevalence of all reported adverse effects and severe adverse effects occurring during the study will be presented in the form of tables.

In addition, summary tables will be presented, that will include data the maximum intensity of the adverse effect, the relationship to the study drug administration and related data on adverse effects as well as patients who discontinued treatment with the study drug due to the occurrence of adverse effects.

It is considered that related adverse effects occurring during the use of the study drug are any adverse effects that occur during an active study phase if:

They were not present prior to the first dose of study medication

or

• They were present prior to receiving the first dose of study drug, but its severity has been increasing during the observation.

All adverse effects occurring during the use of the study drug will be noted in the tables of adverse effects. Other medications used to treat concomitant diseases will be coded in accordance with the WHO Medication Coding Dictionary and will be summarized with the number and percentage of patients receiving concomitant medications and these patients will be grouped according to the pharmacological class of the medicine and International Non-proprietary Name (INN) of the drug.

10.5. Factors which may affect the statistical analysis and modify the results of the Study

- The Patients failure to report on the scheduled control visit
- The discontinuation of the study drug use for reasons other than adverse effects,
- Use other drugs during observation,

Study number: EUP/HED/008/2016

VERSION DATE: 21.11.2016

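### The concomitant-medication table in section 10.4.3 is worded for drugs treating concomitant diseases only, and the same section defines related adverse effects by timing alone, so the part played by drugs given for the cough infection is not made visible

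*Protocol*

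**What the plan says.** The rule for co-medication stands in Protocol section 10.4.3: "Other medications used to treat concomitant diseases will be coded in accordance with the WHO Medication Coding Dictionary". The sentence continues that these "will be summarized with the number and percentage of patients receiving concomitant medications", grouped by pharmacological class and INN.

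Other sections are broader:

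- **Section 2.1, item 4** makes concomitant treatment part of the efficacy assessment, in two parts: "The inclusion of an antibiotic" and "The inclusion of other medications and dietary supplements".
- **Section 8.4** sets no limit by indication: "Data on other drugs used concomitantly with the HEDUSSIN® medicinal product will be recorded in the Study Questionnaire (SQ) during each control assessment".
- **Section 6.1 (Table 1) and section 6.2.1** list treatment of comorbidities and concomitant treatment as two separate items. Table 1 and sections 6.2.1 and 6.2.2 collect concomitant treatment at both visits.

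On adverse effects, section 10.4.3 classes an effect in the active study phase as related if it meets one of two conditions. The first is "They were not present prior to the first dose of study medication"; the second is that it was already present and worsened during observation. The same section also promises tables of the relationship of effects to the study drug.

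**The concern.** Two defects sit in one section, and each makes the other harder to see.

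The first is scope. An antibiotic, antipyretic or supplement given for the cough infection is not, on the plain words, treatment of a concomitant disease. The one co-medication table with a stated coding rule therefore misses the drugs most closely tied to the illness under study.

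The second is the definition of related. It looks only at when an effect appeared or worsened and takes no account of what else the child was taking. A reaction to an antibiotic started after the first dose of syrup meets it.

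Section 1.2 labels "nausea, vomiting, diarrhoea" as common reactions to the syrup, and hives and rash among the uncommon ones. None of these is specific to the syrup. All children in the study take it, so there is no comparator against which to read the frequencies, and section 10.6 presents the result as the frequency of adverse effects of the drug. A reader of the report would want to know how many of the affected children were also on an antibiotic.

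**Working it through.** No arithmetic applies: the plan states no figure on this point, and none depends on it. The check sets the sections side by side.

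**Step 1: does the protocol treat the two kinds of drug as different?** Yes. Table 1 in section 6.1 has one row for comorbidities and their treatment and another entry for concomitant treatment. Section 6.2.1 repeats the split, with long-term medication for comorbidities as one item and concomitant treatment as another. Section 2.1, item 4, shows what the second item is meant to hold: antibiotics, other medications and supplements.

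**Step 2: which kind does the rule in 10.4.3 name?** Its subject is drugs for concomitant diseases, which matches the comorbidity item. Its later words, "will be summarized with the number and percentage of patients receiving concomitant medications", use the broader term. The sentence is thus at odds with itself: the subject is narrow and the count is broad.

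**Step 3: does another section fill the gap?** Not explicitly.

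- Sections 7.1.1 and 10.2 list the efficacy variables without concomitant treatment, although section 2.1 includes it.
- Section 10.4.1 covers previous treatment, not treatment during observation.
- Section 10.4 says that in general all data are summarised descriptively. That would permit a summary of antibiotics, but it gives no coding or grouping rule.
- Section 10.5 names use of other drugs during observation as something that may modify the results, so the protocol recognises the issue.

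**Step 4: does the table's scope affect how adverse effects are attributed?** No. A count of children by drug class and INN assigns no event to any drug. Adding antibiotics to it would leave every adverse-effect table unchanged.

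**Step 5: what does affect attribution?** The timing definition does. Consider a child with no diarrhoea at Visit 1 who starts the syrup and an antibiotic and then develops diarrhoea. The effect was absent before the first dose of syrup, so it is related under section 10.4.3 whatever the antibiotic's part in it. The relationship tables promised in the same section could separate such a case if they rest on the investigator's judgement. The section does not say so, and its own definition of related points the other way.

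**Step 6: would any table specified in the protocol show the overlap?** No. None sets adverse effects against co-medication.

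**The case against.** The strongest reply is that this is loose wording and not a loss of data. Drugs for the infection are a named element of the main aim, are recorded at both visits and fall under the general summary rule in section 10.4. Nothing in section 10.4.3 tells the analyst to exclude them, and the sentence itself goes on to count concomitant medications in general. This stands: a reader might infer that antibiotics disappear from the report, and the documents do not support that. What they support is that these drugs lie outside the stated subject of the one specified table.

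A reader might also infer that the narrow table makes antibiotic reactions appear as syrup reactions. That does not follow, since a drug count attributes nothing. Any misattribution comes from the timing definition, which is a separate defect.

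Nor is misattribution certain. Sections 3.2 and 9 and Table 1 ask for effects caused by or related to the syrup, so an investigator who blames the antibiotic may not report the event at all. That reporting route and the timing definition do not fit together. The reply therefore lowers the likely size of the problem but leaves the inconsistency in place.

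Finally, a split of adverse effects by antibiotic use is detail that often goes in an analysis plan, which is not shown, and section 10.4.3 describes the safety analysis as general and auxiliary. This is fair as regards the extra table. It does not answer the rule and the definition that the protocol does state: a plan that follows them faithfully inherits both.

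**Conclusion.** The point holds as a minor one, in two parts. The stated scope of the co-medication table in section 10.4.3 does not match what sections 2.1, 6.1, 6.2 and 8.4 name and collect. Separately, the timing-only definition of related allows a reaction to a co-administered drug to be counted as related to the syrup, with no table specified in the protocol to reveal it.

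No numerical size can be given. The protocol states neither how many children will receive an antibiotic nor how often they will react to it. A reader might infer that co-treatment could push the syrup's reactions across the 1/100 boundary between uncommon and common. The documents do not support that either: the boundary applies to each reaction separately, nausea, vomiting and diarrhoea are already labelled common in section 1.2, and no rate is available for the skin and allergic reactions. Nor do they support saying that the safety results cannot be interpreted at all.

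The conclusion rests on reading the phrase about concomitant diseases literally, and on the protocol alone. An analysis plan could already contain a broader table, but the protocol text would still need aligning.

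**What to change.** Make three edits to section 10.4.3:

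1. Replace the opening subject of the coding sentence with: *All medications and dietary supplements other than HEDUSSIN used between Visit 1 and Visit 2, whatever the indication*.
2. Rename the category defined by timing as *treatment-emergent*, and keep it distinct from the investigator's assessment of relationship to the drug, which is then tabulated on its own.
3. Add one descriptive table of gastrointestinal and skin/allergic effects for children with and without an antibiotic. State beside it that the split is non-randomised and that denominators may be small. Children given an antibiotic may be sicker, so the table shows the overlap but does not separate the effect of the antibiotic from that of the syrup.

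The cost is a few changed sentences, some extra coding and one more table. Concomitant treatment is already collected at both visits and adverse effects at Visit 2, so no procedure is added for patients.

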11. MONITORING PROCEDURES

The Investigator is responsible for the validation of all data collected in the centre.

In this study, the patients should not be subjected to any additional diagnostic procedures and monitoring. The completeness of the Study Questionnaire (SQ) will be checked at the Office of the Study Organizer and any missing or inconsistent data will be clarified with the Investigator by the people involved in data management.

12. MANAGEMENT OF THE STUDY

12.1. Inspections and audits

Not applicable.

12.2. The scope of the data collected

The Investigator is required to record all the data relating to the procedures detailed in the Study Protocol, including use of the study drug in the Study Questionnaires provided for the purpose of this study.

The Investigator is required to sign the page of the SQ relating to the completion of study and a certificate of study completion to prove that all entered data is accurate and complete.

Any corrections in the SQ and source documents must be placed in such a way that the original entries were still legible (strikethrough single thin line). If the reason for the change is not obvious, this should be clearly stated.

12.3. Verification of the source data

STUDY

Not applicable.

12.4. Verification of data quality

The Study Questionnaires (SQ), transferred from the Study centre to the Office of the Study Organizer will be analysed in terms of completeness, consistency, clarity and compliance with the Protocol.

If data elements are missing from the Study Questionnaires, the Investigator should state the reason for the missing data or other deviations from the Protocol. The Office of the Study Organizer will communicate to the Investigator any questions regarding the processing of data and the points that have not been sufficiently explained, for the purpose of clarification or improvement. The Investigator must ensure that all requests for clarification of data are immediately addressed. The Investigator is obliged to keep copies of all data, including a record of all changes and clarifications in the Study Questionnaire.

12.5. Data management

Data management will be conducted by the Office of the Study Organizer (CRO).

All the procedures of data processing will be carried out in accordance with standard operating procedures of the Office of the Study Organizer.

The Office of Study Organizer has an obligation to ensure that appropriate input methods (e.g. double data entry) are applied, and that all inquiries on missing or inconsistent data are addressed.

In addition, during the formation of the database, rules for creating a database allowing to avoid mistakes during the statistical analysis will be included, such as:

- 1. Entering data as numerical variables in all cases where this is possible.
- 2. Variable names are clearly described, so as not to raise questions during their use in statistical analysis.
- 3. One variable will be assigned to one column.
- 4. The data of each study subjects are entered in the same order and the method of recording missing data will be consistent.
- 5. Each respondent will be given their own, unique identification number.
- 6. The data of all respondents will be entered into a single database.
- 7. Source qualitative variables will be introduced.
- 8. The project database will be consulted with a biostatistics specialist prior to their introduction.
- 9. The data will be entered by one person, and then verified by a second.

12.6. Committee for Study management

Not applicable.

12.7. Archiving and storage of databases

The data will be stored by the Study Organizer for the whole period of 5 years.

13. ADMINISTRATIVE PROCEDURES

13.1. Consent of the relevant authorities to carry out this study

In accordance with paragraph 36u of the Act No. 2 of 6 September 2001 r. on Pharmaceuticals and on Amendments to Some Related Acts (the Act on Pharmaceuticals), published in Journal of Laws 2001 No. 126, item 1381, The Study Protocol does not require the approval from President of the Office for Registration of Medicinal Products, Medical Devices and Biocidal Products and consent for conducting the study as it is a drug efficacy study (PAES) and not a drug safety study (PASS).

The Ethics Committee approval is not needed for this study because it is a non-interventional study. Due to the same reason formal patient consent is not needed. Moreover, the Patient's consent is not needed as the gathered data will contain the Patient's initials only, which does not permit their identification.

13.2. Rules of publication

Determined separately.

Study number: EUP/HED/008/2016

VERSION DATE: 21.11.2016

13.3. Report on the Study

The report on the study will be prepared by the Office of the Study Organizer.

13.4. Details concerning contracts and financing

Contracts with the Investigators will be concluded by the Office of the Study Organizer.

13.5. The insurance, taking responsibility and compensation

The Study Participants are not covered by any additional insurances.

14. AMENDMENTS TO THE PROTOCOL

Amendments can be made by the Office of the Study Organizer and need to be approved by the sponsor.

